## **Response Criteria**

### **Evaluation of Target Lesions**

**Complete Response (CR):** Disappearance of all target lesions. Any pathological lymph nodes (whether target or non-target) must have reduction in short axis to <10 mm.

**Partial Response (PR):** At least a 30% decrease in the sum of the diameters of target lesions, taking as reference the baseline sum diameters.

**Progressive Disease (PD):** At least a 20% increase in the sum of the diameters of target lesions, taking as reference the smallest sum on study (this includes the baseline sum if that is the smallest on study). In addition to the relative increase of 20%, the sum must also demonstrate an absolute increase of at least 5 mm. (Note: the appearance of one or more new lesions is also considered progressions).

**Stable Disease (SD):** Neither sufficient shrinkage to qualify for PR nor sufficient increase to qualify for PD, taking as reference the smallest sum diameters while on study.

**Evaluation of Non-Target Lesions**

**Complete Response (CR):** Disappearance of all non-target lesions and normalization of tumor marker level. All lymph nodes must be non-pathological in size (<10 mm short axis).

Note: If tumor markers are initially above the upper normal limit, they must normalize for a patient to be considered in complete clinical response.

**Non-CR/Non-PD:** Persistence of one or more non-target lesion(s) and/or maintenance of tumor marker level above the normal limits.

**Progressive Disease (PD):** Appearance of one or more new lesions and/or *unequivocal progression* of existing non-target lesions. *Unequivocal progression* should not normally trump target lesion status. It must be representative of overall disease status change, not a single lesion increase.

Although a clear progression of “non-target” lesions only is exceptional, the opinion of the treating physician should prevail in such circumstances, and the progression status should be confirmed at a later time by the review panel (or Principal Investigator).

Any responses must be confirmed by repeat tumor assessment at least 4 weeks after initial documentation. Any suspected progression with < 25% increase in tumor size or the appearance of new lesions will not immediately count as progression but will be evaluated according to irRC (see below).

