### Immune-related Endpoints

The irRC incorporates several elements reflecting the complex tumor dynamics of ipilimumab treatment. Under these criteria, a measure of tumor volume is used that incorporates the contribution of new measurable lesions. Each net percentage change in tumor burden per assessment using irRC accounts for the size and growth kinetics of both old and new lesions as they appear. New lesions alone do not qualify as irPD.

In this study, irRC will be used to assess subject response to study treatment per investigator assessment. The endpoint irPFS will be determined based on investigator assessment. In order to adequately address this objective, investigators will obtain confirmatory scans beyond RECIST PD and follow the instructions in this section for the determination of immune-related response.

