### New Lesion Measurement

The irRC are tumor assessment criteria that have been developed to better capture the activity of immunotherapeutic agents. These criteria have been used with success in clinical studies that were performed with ipilimumab in advanced metastatic melanoma and in lung cancer.

Additional tumor response data will be collected, beyond what is required to apply the RECIST criteria. More specifically, the investigator will have to record in the CRF the bi-dimensional measurements for each new lesion which has become measurable in each tumor assessment.

To support evaluation of progression-free survival based on irRC criteria (irPFS) in this indication, investigators must perform tumor assessments (including new lesion measurements) during the Toxicity/Progression Follow-up Phase in subjects who have experienced RECIST progression until the total sum of product diameters (SPD including new lesions) has increased 25% or more from the nadir or until subjects discontinue study therapy regardless of whether the subject is initiating subsequent therapy. All available post RECIST progression tumor imaging- based assessments during this phase in the study must be entered into the CRF, including any standard of care assessments and any assessments performed while under non-study subsequent cancer therapy.

Any subject who develops an objective tumor response (CR or PR) or progression (PD) is required to undergo confirmatory scans no less than 4 weeks since the prior scan in order to verify the reliability of the radiologic finding. Sites are encouraged to collect additional CT scans after RECIST PD has been confirmed, as long as a subsequent line of therapy has not been initiated.

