### **Efficacy Analyses**

The primary efficacy endpoint is PFS, where disease progression is defined according to RECIST v1.1. Progression free survival will be summarized using the Kaplan-Meier method of estimation, including the 25th, 50th, and 75th percentiles of time to progression with 95% confidence intervals. Kaplan-Meier plots will be produced by disease status strata to examine the difference in response rates between treatment groups. A stratified log rank test will be applied to test for treatment effect on PFS.

Overall response rate is defined as subjects with a best overall response of at least stable disease. Subjects' best overall response, as determined by the investigator from RECIST, will be summarized by presenting the numbers and percentages of subjects in each response category. The overall response rate will be summarized similarly. Ninety-five percent confidence intervals (CIs) will be constructed for the overall response rate.

The duration of overall response is measured from the time measurement criteria are met for CR or PR (whichever is first recorded) according to RECIST v1.1 until the first date that recurrent or progressive disease is objectively documented (taking as reference for progressive disease the smallest measurements recorded since the treatment started). Duration of overall response will be analyzed in a similar manner to PFS.

Duration of stable disease is measured from the start of the treatment until the criteria for progression are met according to RECIST v1.1, taking as reference the smallest measurements recorded since the treatment started, including the baseline measurements. Duration of stable disease will be analyzed in a similar manner to PFS.

Overall survival is defined as the time to death or last contact and will be summarized in a similar manner to PFS.

As additional secondary endpoints, analysis of PFS, overall response rate, duration of overall response, and duration of stable disease will be repeated using the irRC criteria to identify disease response.

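### A sentence among the RECIST criteria says new lesions do not immediately count as progression, while primary PFS uses RECIST v1.1; nothing confines that sentence to the secondary irRC endpoints

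*Combined protocol and SAP*

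**What the plan says.** Section 12.3 (Efficacy Analyses) sets the primary event: "The primary efficacy endpoint is PFS, where disease progression is defined according to RECIST v1.1". It places the irRC analysis elsewhere: "As additional secondary endpoints, analysis of PFS, overall response rate, duration of overall response" and duration of stable disease are repeated under irRC.

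Section 9.1 gives the RECIST rules. Under Evaluation of Target Lesions, "the appearance of one or more new lesions is also considered progressions". Under Evaluation of Non-Target Lesions, progressive disease begins with "Appearance of one or more new lesions and/or" unequivocal progression of existing non-target lesions. The overall-response tables for measurable and for non-measurable disease both assign PD to any new lesion.

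The non-target subsection then closes with a different rule: "Any suspected progression with < 25% increase in tumor size or the appearance of new lesions will not immediately count as progression". It adds that such cases are evaluated under irRC. Under Immune-related Endpoints, "New lesions alone do not qualify as irPD".

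**The concern.** The closing sentence contradicts the PD definition a few lines above it, in the same subsection, and it names no endpoint. Read literally, it governs what counts as progression in general, and so reaches the primary event. A site that follows it could hold back a new-lesion event that a statistician following Section 12.3 would count at once. The same patient could then have two different PFS dates.

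This is more than a missing detail. It is a written rule that would misdate or drop primary events if applied as it stands. Imaging is also tied to progression: under the follow-up rules at the end of Section 8, scans are 3-monthly until progression and follow standard of care afterwards.

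**Working it through.** **1. The plan's own figure.** Section 12.1 gives 96 events, two-sided alpha 0.20, and 70% and 80% power at hazard ratios 0.6895 and 0.6435. With Schoenfeld's formula, power = Φ(½√96 · |ln HR| − 1.2816):
- HR 0.6895: 4.899 × 0.3718 − 1.2816 = 0.540, power 70.5%.
- HR 0.6435: 4.899 × 0.4408 − 1.2816 = 0.878, power 81.0%.

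The stated power reproduces. The point disputes no number; it concerns what counts as one of the 96 events.

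**2. Which scans are affected.** Deferral matters only where a scan is RECIST PD but not irPD. Section 9.1 defines irPD as a rise of at least 25% in irSPD over its nadir, with measurable new lesions included, or any new measurable lesion when the nadir is 0.

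| Finding on the scan | RECIST v1.1 | irRC, same scan | Exposed to deferral |
|---|---|---|---|
| New measurable lesion, irSPD up ≥25% over nadir | PD | irPD | No |
| New measurable lesion, irSPD up <25% | PD | not irPD | Yes |
| New non-measurable lesion only | PD | not irPD | Yes |
| Unequivocal non-target progression, irSPD up <25% | PD | not irPD | Yes |
| Target diameters up ≥20% (and ≥5 mm), under the 25% thresholds | PD | not irPD | Yes |
| Patient with no apparent disease (NAD), new measurable lesion, nadir 0 | PD | irPD | No |
| NAD patient, non-measurable recurrence | PD | not irPD | Yes |

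Two examples show the boundaries:
- A new 10 × 10 mm lesion adds 100 mm². With the other lesions at their nadir, it is irPD on the same scan when the nadir irSPD is 100 / 0.25 = 400 mm² or less. Above that it is RECIST PD only.
- A single target lesion growing 20% along one diameter raises its product by 20%, below 25%. Growing 20% along both diameters raises it by 1.2 × 1.2 − 1 = 44%, which is irPD. The growth clause therefore catches fewer cases than the new-lesion clause might.

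**3. Delay for one patient.** Section 9.1 requires a confirmatory scan at least 4 weeks after the prior scan and schedules assessments about every 3 months. Against the 3-month control median in Section 12.1:
- Deferred to the earliest confirming scan: 28 / 91.3 days = 0.31 of that median.
- Deferred to the next scheduled scan: 3 / 3 = 1.00.
- Dated back to the first scan: 0.

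**4. Effect on a group median (assumed shares).** The documents give no share of deferred events. With exponential times, a 3-month median and 10% to 50% of events deferred, the median becomes 3.1 to 3.5 months for a 4-week delay and 3.4 to 4.8 months for a 3-month delay.

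**5. Between arms (hypothetical only).** Null simulation: 50 per arm, stratified log-rank test, 3-monthly scans, censoring at 36 months, two-sided alpha 0.20. Strata of 70/15/15 are assumed, with medians of 3/3/3 or 3/6/12 months. Two-sided rejection rates:

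| Deferral, vaccine vs control arm | 3-month delay | 4-week delay |
|---|---|---|
| None | 0.201–0.210 | 0.201–0.210 |
| 20% vs 10% | 0.230–0.241 | 0.208–0.212 |
| 30% vs 10% | 0.276–0.309 | 0.212–0.217 |
| 30% vs 30% | 0.203–0.206 | 0.199–0.206 |

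Inflation needs unequal deferral. With 30% vs 10% deferral but events dated back to the first scan, the rate is 0.197–0.206.

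**The case against.** The strongest reply is that the two tracks are already separate. The closing sentence itself points to irRC. Section 9.1 applies both criteria at every assessment. Under Immune-related Endpoints, "investigators will obtain confirmatory scans beyond RECIST PD", and New Lesion Measurement asks for continued assessments "in subjects who have experienced RECIST progression until the total sum of product diameters" has risen by 25%. Both presuppose that RECIST progression has already been recorded. Section 12.3 governs the analysis and makes irRC PFS secondary. Measurable new lesions are also entered in the CRF, so many RECIST dates could be rebuilt.

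Most of this stands. It shows which reading the authors probably intended and limits the damage. It does not remove the conflict, because no text limits the closing sentence to irRC endpoints. CRF measurement of new lesions covers only those that have become measurable, whereas several exposed cases are non-measurable.

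A reader might infer that every scan showing a new lesion would be deferred. The irPD definition does not support that: a measurable new lesion that raises irSPD by at least 25%, or that appears when the nadir is 0, is progression under both criteria on the same scan.

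A reader might also infer that the plan offers no guidance on dating. That is too strong. Duration of response ends at first objective documentation and is analysed like PFS, and one FDG-PET situation is dated to the initial abnormal scan. These point to the first scan, though none is stated as a rule for PFS. The Missing Data paragraph leaves imputation rules to a statistical analysis plan, so on dating alone this is closer to missing detail.

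**Conclusion.** The point holds as an unreconciled rule for the primary event and should be fixed before analysis. Section 12.3 and the RECIST definitions count a new lesion as progression; the closing sentence of the non-target criteria says it does not immediately count. The context favours the RECIST reading, but an investigator could reasonably follow the sentence.

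The documented size is per patient: at least 4 weeks, or about 3 months if the next scheduled scan is awaited, and only for scans that are RECIST PD without irPD. How many such scans there will be is not given.

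It is tempting to conclude that this open-label trial is biased towards the vaccine arm. The documents do not support that. They give no deferral rates and no reason why rates would differ by arm, and equal deferral leaves the error rate essentially unchanged. The simulated figures only illustrate what unequal deferral would do.

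**What to change.** In Sections 9.1 and 12.3, state that:
- the closing sentence of the non-target criteria applies only to the irRC (secondary) endpoints;
- primary PFS counts any RECIST 1.1 progression, including new lesions and recurrence in NAD patients, whatever the later irRC reading;
- the event is dated at the first scan meeting RECIST progression, in line with the first-documentation wording already used for duration of response;
- irRC PFS remains secondary.

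Carry the same wording into the SAP and CRF instructions. Section 4.4 also allows growth of up to 25% early in treatment before a patient goes off study. That wording and the closing sentence must be reconciled with the endpoint definition; no treatment rule is proposed here.

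The cost is text only, with no extra scans, readers or patients.

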**Evaluation of Best Overall Response**

The best overall response is the best response recorded from the start of the treatment until disease progression/recurrence (taking as reference for progressive disease the smallest measurements recorded since the treatment started). The patient's best response assignment will depend on the achievement of both measurement and confirmation criteria.

**For Patients with Measurable Disease (i.e., Target Disease)**

Target Lesions	Non-Target Lesions	New Lesions	Overall Response	Best Overall Response when Confirmation is Required*
CR	CR	No	CR	≥4 wks. Confirmation**
CR	Non-CR/Non-PD	No	PR	≥4 wks. Confirmation**
CR	Not evaluated	No	PR	
PR	Non-CR/Non-PD/not evaluated	No	PR	
SD	Non-CR/Non-PD/not evaluated	No	SD	documented at least once ≥4 wks. from baseline**
PD	Any	Yes or No	PD	no prior SD, PR or CR
Any	PD***	Yes or No	PD	
Any	Any	Yes	PD	

\* See RECIST 1.1 manuscript for further details on what is evidence of a new lesion.

\*\* Only for non-randomized trials with response as primary endpoint.  
 \*\*\* In exceptional circumstances, unequivocal progression in non-target lesions may be accepted as disease progression.

Note: Patients with a global deterioration of health status requiring discontinuation of treatment without objective evidence of disease progression at that time should be reported as “*symptomatic deterioration.*” Every effort should be made to document the objective progression even after discontinuation of treatment.

### For Patients with Non-Measurable Disease (i.e., Non-Target Disease)

Non-Target Lesions	New Lesions	Overall Response
CR	No	CR
Non-CR/non-PD	No	Non-CR/non-PD*
Not all evaluated	No	not evaluated
Unequivocal PD	Yes or No	PD
Any	Yes	PD
* ‘Non-CR/non-PD’ is preferred over ‘stable disease’ for non-target disease since SD is increasingly used as an endpoint for assessment of efficacy in some trials so to assign this category when no lesions can be measured is not advised		

### Duration of Response

Duration of overall response: The duration of overall response is measured from the time measurement criteria are met for CR or PR (whichever is first recorded) until the first date that recurrent or progressive disease is objectively documented (taking as reference for progressive disease the smallest measurements recorded since the treatment started).

Duration of stable disease: Stable disease is measured from the start of the treatment until the criteria for progression are met, taking as reference the smallest measurements recorded since the treatment started, including the baseline measurements.

### Immune-related Endpoints

The irRC incorporates several elements reflecting the complex tumor dynamics of ipilimumab treatment. Under these criteria, a measure of tumor volume is used that incorporates the contribution of new measurable lesions. Each net percentage change in tumor burden per assessment using irRC accounts for the size and growth kinetics of both old and new lesions as they appear. New lesions alone do not qualify as irPD.

In this study, irRC will be used to assess subject response to study treatment per investigator assessment. The endpoint irPFS will be determined based on investigator assessment. In order to adequately address this objective, investigators will obtain confirmatory scans beyond RECIST PD and follow the instructions in this section for the determination of immune-related response.

### New Lesion Measurement

The irRC are tumor assessment criteria that have been developed to better capture the activity of immunotherapeutic agents. These criteria have been used with success in clinical studies that were performed with ipilimumab in advanced metastatic melanoma and in lung cancer.

Additional tumor response data will be collected, beyond what is required to apply the RECIST criteria. More specifically, the investigator will have to record in the CRF the bi-dimensional measurements for each new lesion which has become measurable in each tumor assessment.

To support evaluation of progression-free survival based on irRC criteria (irPFS) in this indication, investigators must perform tumor assessments (including new lesion measurements) during the Toxicity/Progression Follow-up Phase in subjects who have experienced RECIST progression until the total sum of product diameters (SPD including new lesions) has increased 25% or more from the nadir or until subjects discontinue study therapy regardless of whether the subject is initiating subsequent therapy. All available post RECIST progression tumor imaging- based assessments during this phase in the study must be entered into the CRF, including any standard of care assessments and any assessments performed while under non-study subsequent cancer therapy.

Any subject who develops an objective tumor response (CR or PR) or progression (PD) is required to undergo confirmatory scans no less than 4 weeks since the prior scan in order to verify the reliability of the radiologic finding. Sites are encouraged to collect additional CT scans after RECIST PD has been confirmed, as long as a subsequent line of therapy has not been initiated.

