## **2.5 PD-1 Checkpoint Inhibitors (Nivolumab and Pembrolizumab)**

Two anti-programmed death 1 (PD-1) antibodies, nivolumab and pembrolizumab, were approved in 2014 by the Food and Drug Administration for the treatment of metastatic melanoma after progression during ipilimumab treatment and, in patients with BRAF-mutated melanoma, after progression during treatment with a BRAF inhibitor. These antibodies were associated with objective responses in 30 to 40% of patients. Two phase 3 trials have shown superior efficacy of nivolumab, as compared with chemotherapy, in previously untreated patients with wild-type BRAF tumors or in patients with either mutant or wild-type BRAF tumors after progression during ipilimumab therapy and, in patients with tumors positive for BRAF mutation, after progression during treatment with a BRAF inhibitor (Robert C, NEJM, 2015 and Weber JS, Lancet, 2015). Recently, pembrolizumab was associated with longer progression-free survival and overall survival and higher response rates than those associated with ipilimumab in a phase 3 trial involving patients with advanced melanoma (Robert C, NEJM, 2015).

In May 2015, results from the CheckMate 067 trial were presented. This study involving patients with previously untreated advanced melanoma, treatment with nivolumab alone or with the combination of nivolumab and ipilimumab resulted in significantly longer progression-free survival and higher objective response rates than did treatment with ipilimumab alone. The incidence of adverse events in this study was, in general, lowest in the nivolumab group and highest in the combination group.

Pembrolizumab was first evaluated in the large, phase 1 KEYNOTE-001 study (Robert C, Lancet, 2014). In a pooled analysis of 411 patients with advanced melanoma enrolled in KEYNOTE-001 and after a median follow-up duration of 18 months, the response rate was 34%, the response was maintained in 81% of those patients, and median overall survival was 25.9 months (Ribas A, 2014)

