## 3 PATIENT SELECTION

### 3.1 Eligibility criteria

Must be confirmed within 30 days prior to study enrollment/registration, except for  $\beta$ -HCG (confirm within 1 week) when appropriate. Subjects who are positive (+) for the BRAF mutation who have not received BRAF inhibitors yet, may be enrolled to this study based on the discretion of the treating physician and may receive BRAF inhibitors following this study.

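### Scans taken under a later cancer drug feed the secondary irRC endpoints, and no rule stops irRC evaluation when that drug starts

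*Combined protocol and SAP*

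**What the plan says.** Section 9.1, Immune-related Endpoints, gives the purpose: the irRC are used to assess response to study treatment, by investigator assessment. It adds that new lesions alone are not irPD.

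Under New Lesion Measurement, data collection is introduced with "To support evaluation of progression-free survival based on irRC criteria (irPFS) in this indication". Assessments after RECIST progression must be performed until the sum of products has risen 25% or more from nadir or study therapy stops, whether or not another therapy is being started. Entry is a separate rule: "All available post RECIST progression tumor imaging- based assessments during this phase in the study must be entered into the CRF". That rule is then widened to scans outside the trial's own treatment, by the words "including any standard of care assessments and any assessments performed while under non-study subsequent cancer therapy". The last sentence there encourages extra CT scans after confirmed RECIST progression, but only "as long as a subsequent line of therapy has not been initiated".

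Definition of Tumor Response Using irRC calculates irSPD at every post-randomisation assessment collected and uses the lowest value as the nadir for classifying later ones. An irPR is a fall of 50% or more from baseline, with no condition on current therapy.

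The evaluation window is set by "The best overall response is the best response recorded from the start of the treatment until disease progression/recurrence". Both durations also run to progression. In Section 12.3, Efficacy Analyses, PFS, overall response rate and the two durations "will be repeated using the irRC criteria to identify disease response". OS is not among the repeated endpoints. Missing Data gives one censoring rule for time-to-event endpoints (time 0 for patients with no evaluations) and leaves imputation rules to a statistical analysis plan.

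**The concern.** The irRC endpoints are the protocol's means of seeing delayed immune benefit. If tumour shrinkage under a different drug counts, they describe the randomised treatment plus whatever followed it, which is not the stated purpose.

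Later active treatment is foreseeable. Section 3.1 says BRAF-positive patients who have not had a BRAF inhibitor "may receive BRAF inhibitors following this study". On PD-1 antibodies, whose 2014 approval it places after progression on ipilimumab, Section 2.5 says: "These antibodies were associated with objective responses in 30 to 40% of patients". The protocol schemas take progressing patients off study, and Section 8 leaves their later imaging to standard of care, so scans under a second drug will exist for some of them.

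At stake are the irCR and irPR categories, duration of response, irPFS and duration of stable disease by irRC.

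**Working it through.** **The plan's own figure.** No figure is stated for any irRC endpoint. The one stated for primary RECIST PFS (Section 12.1) is 96 events, for 80% power at a hazard ratio of 0.6435 and two-sided alpha 0.20. By Freedman's formula, events = (1.2816 + 0.8416)² × (1.6435 / 0.3565)² = 4.508 × 21.25 = 95.8, so 96. It reproduces, and this point does not affect it.

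**From scan to endpoint.** Let B be the baseline irSPD of a patient with measurable disease.

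1. A new measurable lesion appears and total irSPD is below 1.25 × B. Under RECIST 1.1 this is progression. Under irRC it is irSD.
2. The patient leaves study therapy and starts another drug. A standard-of-care scan is taken and, if it falls in the follow-up phase, must be entered.
3. irSPD is calculated from that scan. If it is 0.5 × B or less, the irPR definition is met. No irPD has occurred, so the best-response window is still open.
4. Duration of response starts under the later drug. irPFS and duration of irSD continue.
5. The nadir is now at most 0.5 × B, so irPD is called at 1.25 × 0.5 × B = 0.625 × B or less, instead of at 1.25 × B. The later drug therefore also moves the threshold for the irPD date.

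No step is blocked by a rule on new therapy in Section 9.1 or in Section 12.3, Efficacy Analyses or Missing Data.

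**Which endpoints move.** Section 12.3 defines overall response rate as a best response of at least stable disease. The patient in step 1 is already irSD and already counts, so step 3 changes the category and barely changes that rate.

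**Size in the irCR/irPR categories.** Inputs: 50 patients per arm (Section 12.1); response to the later drug 30% to 40% (Section 2.5, borrowed as an assumption); patients per arm switching after RECIST progression and before irPD, 5 to 10 (assumption).

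- Low: 5 × 0.30 = 1.5 patients; 1.5 / 50 = 3 percentage points.
- High: 10 × 0.40 = 4 patients; 4 / 50 = 8 percentage points.
- Each further switcher adds 0.30 to 0.40 of a patient, or 0.6 to 0.8 points. With 20% to 60% of an arm switching (10 to 30 patients), the range is 3 to 12 patients, or 6 to 24 points.

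**Illustration for irPFS, on assumed inputs only.** The two arms have no true difference. RECIST PFS is exponential with median 3 months, followed by an exponential time to irPD with mean 3 months. Switchers change drug at RECIST progression, and the new drug multiplies their remaining time to irPD by 2 or 3. Simulated median irPFS in months:

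| Share switching, arm 1 / arm 2 | Time doubled | Time tripled |
|---|---|---|
| 0% / 0% | 6.1 v 6.1 | 6.1 v 6.1 |
| 30% / 30% | 6.7 v 6.7 | 7.1 v 7.1 |
| 20% / 50% | 6.5 v 7.2 | 6.8 v 8.0 |
| 50% / 20% | 7.2 v 6.5 | 8.0 v 6.8 |

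Equal switching raises both medians and creates no difference. Unequal switching creates one, in either direction. Shares of 20% to 50% are 10 to 25 patients per arm, at or above the 5 to 10 used for the response categories.

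**The case against.** Much of the case on the other side stands.

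- Mandatory scanning has a stop: a 25% rise or the end of study therapy. The entry rule covers scans within the Toxicity/Progression Follow-up Phase, which is defined nowhere, so it is unclear how many scans of a patient who has left study therapy fall inside it. But the rule expressly names scans under non-study therapy, so some must.
- A reader might infer that New Lesion Measurement contradicts itself. It does not: entering scans that exist and encouraging extra scans only before a new line can both be done. The two sentences treat new therapy differently and leave the analysis rule open.
- The window between RECIST progression and irPD is narrower than it looks. Evaluation of Non-Target Lesions says new lesions do not immediately count as progression but are evaluated by irRC, and a confirmatory scan at 4 weeks or later is required. Section 4.4 tolerates mild early progression. For patients with no apparent disease, whose nadir is 0, any new measurable lesion is irPD. The window narrows but stays open for patients with measurable disease.
- Following patients regardless of later therapy is a legitimate treatment-policy analysis for irPFS, and censoring at a switch may be informative. That is a good reason to report both versions. It does not justify crediting a response achieved on another drug to study treatment.
- A separate statistical analysis plan might supply a rule, but what the protocol promises there is imputation rules.

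**Conclusion.** The point holds for the secondary irRC endpoints. Section 9.1 routes scans under later therapy into irSPD and its nadir, and nothing ends irRC evaluation at the switch. Applied as written, a later drug's shrinkage can count as an irPR of the randomised arm, start a duration of response, and extend irPFS and irSD time.

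On the assumed 5 to 10 switchers per arm and 30% to 40% responding, the size is 1.5 to 4 patients, or 3 to 8 percentage points in the irCR/irPR categories. Both inputs are uncertain. The documents give no switching count, and an objective response rate does not translate directly into a 50% fall from the original baseline with new lesions included. Many patients may also already be on a PD-1 antibody, since Section 2.5 notes a shift to those drugs as first-line treatment.

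Three stronger readings are not supported:

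- **Bias known to favour one arm.** The open label, and vaccine continuing to month 24 in Arm 1A when Arm 2A dosing ends on Day 64, make unequal switching plausible. But progressing patients leave study in both arms, and the direction is not determined.
- **Inflated overall response rate.** It counts stable disease, so it is little affected.
- **Damage to the main result.** Primary RECIST PFS, OS and the sample size are not touched, and Section 12.3, Multiplicity Issues, rules out formal tests of secondary efficacy endpoints.

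**What to change.** 1. In Sections 9.1 and 12.3, state that irRC best overall response, and the responses that enter irRC duration of response, use only assessments before the first non-study anticancer therapy.
2. Report irPFS and the irRC durations in two versions: censored at the last assessment before that therapy, and with all scans. Say in advance which is the main one.
3. Record the start date and type of the first non-study anticancer therapy on the CRF.
4. Define the Toxicity/Progression Follow-up Phase, and keep entering all scans obtained.

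The cost is a few sentences, the CRF fields for that therapy and a second run of each time-to-event analysis. No scan or treatment schedule changes. The drawback is that some irPFS and duration events become censored in one version, possibly informatively; the all-scan version covers that.
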